#### Symptoms

- Breathlessness, Couch and Sputum Scale (BCSS)

- EXAcerbations of Chronic Pulmonary disease Tool (EXACT)
- St George's Respiratory Questionnaire for COPD patients (SGRQ-C)
- Use of reliever medication
- Exacerbations

#### Safety

- AEs
- Heamatology
- Clinical chemistry
- Urinalysis
- Vital signs
- 12-lead ECG
- Physical examination

# 2.3 Exploratory objectives

The exploratory objectives are:

- To investigate the effects of AZD9668 on urine desmosine in COPD patients.
- To collect samples for possible retrospective pharmacogenetics analysis to investigate influence of genotypic variation on response.

Exploratory outcome variables aligned to these objectives are:

- Urine biomarkers, including but not limited to desmosine (creatinine normalised).
- Pharmacogenetics, please refer to Appendix D for further details.

None of the exploratory objectives will form part of the Clinical Study Report.

# **3.** STUDY PLAN AND PROCEDURES

This Clinical Study Protocol has been subject to a peer review according to AstraZeneca standard procedures.

# 3.1 Overall study design and flow chart

This is a 12-week randomised, double-blind, placebo-controlled, parallel-group, multi-centre phase IIb study to assess the effect of AZD9668 on structural changes in the airways in COPD patients. The primary variable is AWT-Pi10 assessed by MSCT.

The plan is to enrol approximately 70 patients, men and women aged 50 to 80 years inclusive, to obtain approximately 50 randomised patients. Approximately 15 centres in Canada and Europe are planned to participate in the study with 3 to 10 patients per centre.

There will be 8 visits to the clinic: Visit 1a (enrolment), Visit 1b (screening), Visit 2 (randomisation), Visits 3, 4, 5 and 6 (after 1, 4, 8 and 12 weeks of treatment) and Visit 7 (follow-up).

All inclusion/exclusion criteria that can be assessed at each visit should be checked carefully, including patients suitability to use electronic devices/perform home spirometry, before therapy is changed and before randomisation.

At Visit 1a all patients will be informed about the study and, if willing to take part in the study, sign the informed consent form and have demographic data collected. Signing the informed consent form must be done before any study-related procedures, restrictions or screening assessments are performed. The timing of this visit in relation to Visit 1b will be dependent on the medication being taken by the patient on entry to the study as described in Section 5.5.3.2.

At Visit 1b, all patients must be on tiotropium alone as maintenance therapy. In addition to tiotropium maintenance therapy, patients will be allowed to use short-acting  $\beta_2$ -agonists (SABA) as reliever medication throughout the study. See Section 5.5.3.2 regarding provision of tiotropium and SABA.

At Visit 1b, patients will be screened and evaluated for eligibility to enter the 14-17 day run-in period. Included patients must have a documented COPD history with symptoms for at least 1 year according to GOLD 2008, and they must be ex-smokers with a smoking history of at least 10 pack years. Their FEV1 must be 40 - 70% of the predicted normal value and FEV1/FVC <70%, both values post-bronchodilator.

Included patients will be asked to fill in an electronic diary and to measure  $FEV_1$  and PEF morning and evening from Visits 1b to 6.

To be randomised to the 12-week treatment period a visually acceptable MSCT scan with no clinically relevant abnormal CT findings must have been performed 2 to 7 days before Visit 2. Before the patient has the baseline MSCT scan the laboratory safety results from Visit 1b must be reviewed and considered eligible (refer to exclusion criterion 8). The patient must also show complete morning recordings of daily FEV1 data at least 10 of the last 14 days before Visit 2.

At Visit 2 eligible patients will be randomised to either

- AZD9668, 60 mg twice daily
- placebo to match AZD9668

Two weeks after stopping study medication there will be a follow up visit.

An independent safety review committee will review available safety data, see Section 12.4.

The pharmacogenetic part of the study is described in Appendix D.

Clinical Study Protocol Drug Substance AZD9668 Study Code D0520C00014 Edition Number 1 Date

# Figure 1Study Flow Chart

Run-in Treatment period

Refer to Table 1, Visit Schedule, and Table 2, Study Plan, for further details of visits and assessments.

Table 1	Visit schedule	
Visit No.	Type of Visit	No. of weeks ± no of days between visits
1a	Enrolment Visit	Patients not taking inhaled glucocorticoste- roids (iGCS): before Visit 1b depending on previous medication Patients on iGCS: >3 weeks before Visit 1b
1b	Screening Visit	14-17 days before Visit 2
2	Randomisation Visit	Day 1
3	Treatment visit	1 week $\pm 1$ day after Visit 2
4	Treatment visit	4 weeks $\pm 3$ days after Visit 2

# (Continued)

Table 1	Visit schedule	(Continued)
Visit No.	Type of Visit	No. of weeks ± no of days between visits
5	Treatment visit	8 weeks $\pm 3$ days after Visit 2
6	End of treatment visit	12 weeks -3 days after Visit 2
7	Follow-up Visit	14 weeks ±3 days after Visit 2

Study Visit	Visit 1a	Visit 1b	Visit 2	Visit 3	Visit 4	Visit 5	Visit 6	Visit 7
Written informed consent	х							
Demography (date of birth, sex and race)	X							
Physical examination		х	Х	Х	Х	х	Х	Х
Height/Weight		X					x (weight only)	
Medical/surgical history		х						
COPD history		X						
Smoking history		X						
Smoking habits			Х				X	
MSCT (pre-visit, see Section 6.3.1)			2 to 7 days before Visit 2				0 to 3 days before Visit 6	
Clinical chemistry, haematology and urinalysis b		X	Х	Х	х	X	X	Х
Pregnancy test a		х	Х					х
Inclusion/exclusion criteria	х	х	Х					
Randomisation			х					
Vital signs, 12-lead ECG b		х	x c	Х	Х	х	х	х
Spirometry (FEV 1 , FVC, SVC) b		Х	Х	Х	Х	Х	Х	
Body Plethysmography (IC, TLC, FRC, RV, SGaw) b			X				X	
DL CO b			Х				Х	
Dispense maintenance and reliever drugs	(x)	X	(x)	(x)	(x)	(x)		

#### Table 2Study Plan

### (Continued)

Table 2

Study Visit	Visit 1a	Visit 1b	Visit 2	Visit 3	Visit 4	Visit 5	Visit 6	Visit 7
Administer AZD9668 morning dose at clinic after spirometry			Х	х	x	х	х	
AZD9668/placebo Dispense/ Check/ Return (d/c/r)			d		d / c / r	d / c / r	c / r	
e-PRO / Home spirometry device d training/ dispense/ check/ return (t / d / c / r)	(t)	t / d	С	С	с	С	c / r	
BCSS, EXACT, FEV 1 , PEF and intake of study drugs - assessed at the patient's home		x					X	
SGRQ-C b		(x) e	Х				Х	
Desmosine urine sampling			Х		Х		Х	
Concomitant medications recorded	Х	Х	Х	Х	Х	Х	Х	Х
Adverse events		Х	Х	Х	х	х	х	Х
Exacerbation recording		X	Х	Х	X	Х	Х	X
Pharmacogenetics blood sampling (optional) f			Х					

a Pregnancy tests at Visit 1b and 7 to be taken in blood and pregnancy test at Visit 2 to be taken in urine.

b Assessments to be done pre-dose of AZD9668 at Visits 2-6.

c A second ECG and vital signs measurement should be done 3-4 hours post-dose of AZD9668 at Visit 2.

d ePRO including BCSS and EXACT questionnaires, Questions on intake of study drugs and Spirometry measurements of PEF and FEV1,

e Training session, data not to be collected in study database.

f Only 1 pharmacogenetic sample is required. This should be taken at Visit 2 or any subsequent visit once separate written informed consent has been obtained.

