To minimise the variability of the response to AZD9668 that could occur as a result of patients being on different background medications for COPD, all patients will be standardised to maintenance therapy with tiotropium. This will entail patients on inhaled GCS (including combination therapy with LABA) being withdrawn from that treatment, and switched to tiotropium only. However, this would only be done with the patient's express consent and if the investigator assesses that it is safe to do so. To mitigate the risks associated with inhaled GCS withdrawal, only patients with an FEV1 of  $\geq$ 40 % of predicted normal value will be recruited to this study. Also, as all patients will receive tiotropium, the risk of inhaled GCS withdrawal in a short-term study is considered to be small. Additionally, patients will be closely monitored during the run-in period and throughout the study with daily FEV1 and PEF measurements and symptom diaries. The use of MSCT involves ionizing radiation that increases the risk of radiogenic tumors in patients. The data related to biological effects of CT radiation and recommendations from different committees has been considered in the design of the study (Mayo JR 2008). The risk is known to be age and gender dependant and higher in children, young adults, women, and pregnancy (high radiosensitive group). The risk from radiation exposure is known to be cumulative, and may involve other factors like use of contrast agents. MSCT has been applied in several clinical studies for COPD and asthma and the risk-benefit evaluation has been done, and literature is available. AstraZeneca has considerable experience in appplicaton of CT imaging for COPD and has been involved in population studies and cross sectional studies (Brown RH et al 2005, Coxson HO et al 2008b, Capraz F et al 2007, Lee YM et al 2004). The understanding of the risk – benefit aspects helps in optimising the CT radiation dose to the endpoint. Since the participation in the present study may not offer direct benefit to the patient, a dose constraint will be applied based on ALARA (As Low As Reasonably Achievable) principle. Detailed information on the potential risks of radiation, the aims, methods, benefits and potential hazards of the study will be given to patient during the informed consent process.

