The total radiation dose for the study is expected to be around 10 - 12 mSv. This dose is close to accepted radiation dose for biological research (1 to 10 mSev). In the present study the radiosensitive group has been therefore excluded to a major extent. The older demographic of patients fall into a low risk profile for risk of radiation, and the laboratory safety results from Visit 1b must be reviewed and considered eligible prior to baseline scan to avoid any unnecessary radiation exposure. The selection of patients includes male and female patients aged 50 - 80 years. Each patient will receive 4 scans, 2 scans (a paired inspiratory and expiratory scan) at each visit, 3 months apart. The imaging protocol and study design is based on the EU guidance (See Guidance document). The potential benefits of the study are expected to be Category IIB (aimed directly at the diagnosis, cure or prevention of disease). Since this is a study to establish the feasibility of a clinical trial in COPD evaluated by MSCT the study has not been adequately powered to demonstrate efficacy but only to detect a trend.

The study design chosen for this study is considered to optimal to detect a clinically meaningful effect of AZD9668 while the safety risks are minimised. The benefit/risk balance of using AZD9668 in the present study in patients with COPD can therefore be considered acceptable.

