# 5. STUDY CONDUCT

## 5.1 **Restrictions during the study**

The following restrictions apply:

- Use of disallowed concomitant medication (refer to Section 5.6.3)
- All female patients must have a serum pregnancy test at Visit 1b and Visit 7. Women of child bearing potential must undergo an additional urine pregnancy test at Visit 2 prior to randomisation. Women of child bearing potential must be using highly effective methods of birth control:
  - Total sexual abstinence. Abstinence must be for the total duration of the study.
  - Vasectomised sexual partner (with participant assurance that the partner received post-vasectomy confirmation of azoospermia).
  - Tubal occlusion

٠

- Intra-uterine device (coils must be copper banded)
- Intra-utrine system (IUS) (Levonorgestrel IUS eg, Mirena)
- Medroxyprogesterone injections (Depo-provera)
- Prior to the clinic lung function tests:
- No alcohol within 4 hours
- No vigorous exercise within 2 hours
- No large meals within 2 hours
- No prohibited medication as listed in Section 5.6.3.1

The patient should not start smoking during the study.

- Patients should not donate blood at any time during the study or for 3 months following completion of the study.
- Patients should abstain from taking part in any other study, whilst participating in this study.

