### 5.8.1 **Procedures for discontinuation of a patient from the study**

Patients are at any time free to withdraw from the study without prejudice to further treatment (withdrawal of consent). Such patients will always be asked about the reason(s) and the presence of any adverse events. If possible, they will be seen and assessed by an investigator(s). Adverse events will be followed up (see Sections 6.4.3 and 6.4.4); the eDiary/home spirometry device, investigational product and additional non-investigational study drugs should be returned by the patient.

For patients discontinuing during the enrolment period or run-in period, only assessment for AEs will be performed. The reason for discontinuation should be recorded in the eCRF.

If a patient discontinues participation in the study due to study specific discontinuation criteria no 8 to 11, this should always be recorded as "study specific discontinuation criteria met" on the termination form. In addition, the investigator has to assess whether the discontinuation should also be reported as a discontinuation due to adverse event (DAE) on the AE form.

If a patient discontinues after randomisation he/she should be asked to attend the end of treatment visit, Visit 6, and the follow-up visit, Visit 7. All assessments should be carried out at these visits unless the patient is unwilling to do so, with the exception of MSCT for patients who have had less than 2 months of randomised treatment. The reason for discontinuation will be recorded in the eCRF.

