### 6.3.1 MSCT variables

A baseline MSCT assessment (paired inspiratory and expiratory scan) will be performed 2 to 7 days prior to randomisation (Visit 2) to assess airway wall thickness, lung density and expiratory air trapping. The scan will be done after evaluation of the laboratory safety results from Visit 1b and it will be visually evaluated by a radiologist within 48 hours and prior to randomisation. The scan must be visually acceptable with no artefacts related to motion or streak or metal. If any defects are noted they will be recorded in the CRF and may result in loss of scan and patient. A second assessment will be performed at 0 to 3 days prior to Visit 6.

The performance of each site and scanner will be assessed before the first patient is enrolled.

All sites will be provided with a separate manual containing all necessary instructions for MSCT assessments.

Images will be transferred to a core lab at a CRO for analysis. Images will be analysed by VIDA software and the baseline scans will be double-read for quality check.

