### 6.4.5 Laboratory safety assessment

Blood and urine samples for determination of clinical chemistry, haematology, and urinalysis will be taken at the visits indicated in the Study Plan (see Table 2) and before intake of the morning dose of investigational product. Blood samples will be analysed at a central laboratory. Urinalysis will be performed locally at the study site using dipsticks provided by the central laboratory.

The central laboratory will provide all the materials required for blood and urine sampling. Instructions for labelling, storage and shipping will be detailed in the laboratory manual. The central laboratory will also provide up to date reference ranges throughout the study for the management of patient safety.

Clinically relevant deviations from the reference range in the lab values will be handled as outlined in Section 6.4.3, adverse events based on examinations and tests.

The following laboratory variables will be measured:

Haematology		
Haemoglobin	Mean Cell Volume (MCV)	Platelet count
Erythrocyte count	Mean Cell Haemoglobin (MCH)	Reticulocyte count
Haematocrit	Mean Cell Haemoglobin Concentration (MCHC)	Leucocyte count (absolute and percentage including neutrophil, lymphocyte, monocyte, eosinophil and basophil counts)

Clinical Chemistry			
Creatinine	Potassium	Creatinine kinase (CK) a	
C-Reactive Protein (CRP)	Calcium, total Lactate dehydroger		
Total bilirubin b	Sodium Glucose		
Alkaline phosphatase	Cholesterol	Free thyroxine (T4) (Visit 1b only)	
Aspartate aminotransferase (AST)	Triglycerides	Thyroid stimulating hormone (TSH) (Visit 1b only)	
Alanine aminotransferase (ALT)	Urea	Haptoglobin	
Albumin	Gamma Glutamyltransferase (GGT)	hCG c	

a CKMB fraction to be measured if CK is elevated >2 x ULN (as detailed in the laboratory manual)

b Unconjugated and conjugated bilirubin will be measured if the total bilirubin is elevated

c Visit 1b and Visit 7, only for female patients

For blood volumes see Section 7.1.

Urinalysis		
Protein	Glucose	Haemoglobin

Please refer to Section 5.8 for the discontinuation criteria relating to laboratory safety variables.

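### No pregnancy test is scheduled between Visit 2 and Visit 7, so the second CT pair falls 78–84 days after the last test and no scheduled test during dosing can trigger the stopping rule

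*Protocol*

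**What the plan says.** Inclusion criterion 2 (Protocol Section 4.1) admits women of child-bearing potential. The testing schedule is the same wherever it appears: criterion 2, Section 5.1, Table 2, Section 6.4.5 and Section 6.4.9. Footnote a to Table 2 reads: "Pregnancy tests at Visit 1b and 7 to be taken in blood and pregnancy test at Visit 2 to be taken in urine". The hCG entry in the Section 6.4.5 laboratory panel carries the note "Visit 1b and Visit 7, only for female patients". Section 5.1 adds: "Women of child bearing potential must undergo an additional urine pregnancy test at Visit 2 prior to randomisation". Table 2 marks no pregnancy test at Visits 3, 4, 5 or 6, and the urinalysis done at those visits covers only protein, glucose and haemoglobin.

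On radiation, Section 1.4 describes the risk as "higher in children, young adults, women, and pregnancy (high radiosensitive group"), and for the first scan it requires that "the laboratory safety results from Visit 1b must be reviewed and considered eligible prior to baseline scan to avoid any unnecessary radiation exposure". For the second scan, Section 6.3.1 says only: "A second assessment will be performed at 0 to 3 days prior to Visit 6".

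On study drug, Section 5.5.3.1 puts the first dose at Visit 2 and the last at Visit 6. Section 13.3.1 requires the drug to be stopped at once if a patient becomes pregnant.

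On early stopping, pregnancy is discontinuation reason 6 in Section 5.8. Section 5.8.1 asks patients who stop after randomisation to have all end-of-treatment assessments unless unwilling, "with the exception of MSCT for patients who have had less than 2 months of randomised treatment".

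**The concern.** The start of the study is covered. hCG is part of the Visit 1b laboratory results that must be reviewed before the baseline scan, and a urine test precedes randomisation and the first dose. Nothing comparable precedes the second CT pair, although the Protocol itself places pregnancy in the group at higher radiation risk.

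During dosing, the rule to stop the drug depends on someone noticing or reporting a pregnancy, because no scheduled test can reveal one. The Visit 7 serum test is taken from all women at a point when neither the scan nor the drug exposure can be prevented.

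Section 5.8.1 has a separate drafting gap. Read literally, a woman withdrawn because she is known to be pregnant, after two months or more of treatment, is still directed to the CT pair unless she declines.

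What is at stake is avoidable exposure to radiation and study drug in a rare case. The estimate of the treatment effect is not at stake.

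**Working it through.** The Protocol states no interval between pregnancy test and scan, so there is no figure of its own to reproduce. The intervals follow from the windows in Tables 1 and 2 and Section 6.3.1, counted in days after Visit 2.

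**Inputs**

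- Visit 4: 28 ± 3 = day 25–31
- Visit 5: 56 ± 3 = day 53–59
- Visit 6, with the last dose: 84 − 3 to 84 = day 81–84
- Second CT pair, 0–3 days before Visit 6: 81 − 3 to 84 − 0 = day 78–84
- Visit 7: 98 ± 3 = day 95–101
- Visit 1b: 14–17 days before Visit 2; baseline scan: 2–7 days before Visit 2

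**Intervals under the current schedule**

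| Interval | Calculation | Days |
|---|---|---|
| Visit 1b test to baseline scan | 14 − 7 to 17 − 2 | 7–15 |
| Visit 2 test to second scan | 78 − 0 to 84 − 0 | 78–84 |
| Second scan to Visit 7 test | 95 − 84 to 101 − 78 | 11–23 |
| Last dose to Visit 7 test | 95 − 84 to 101 − 81 | 11–20 |
| Visit 2 test to Visit 7 test | 95 − 0 to 101 − 0 | 95–101 |

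No test is scheduled after the first dose and up to the last. The 78–84 day range applies to patients who follow the schedule. A patient who stops after at least two months could be scanned earlier, from about day 60 (taking two months as 60 days), also without a repeat test.

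**Intervals with dipsticks at Visits 4 and 5 and on the day of the second scan**

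- Visit 2 to Visit 4: 25–31 days
- Visit 4 to Visit 5: 53 − 31 = 22 to 59 − 25 = 34 days
- Visit 5 to scan-day test: 78 − 59 = 19 to 84 − 53 = 31 days
- Scan-day test to scan: 0 days

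The longest gap without a test falls to 34 days. With the scan-day test alone, the test-to-scan gap also falls to 0, but nearly all of the dosing period remains without a test.

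**Expected number of pregnancies.** The Protocol gives no count of women of child-bearing potential and no pregnancy rate, so both inputs are assumptions: 0–3 such women among 50 randomised, and a chance of 0.01%–0.5% each over 12 weeks. The range is 0 × 0.0001 = 0 to 3 × 0.005 = 0.015. The upper end is about one pregnancy in 67 trials of this kind (1 / 0.015 ≈ 67).

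**The case against.** The strongest reply is that the schedule is consistent throughout and that the risk has been dealt with in other ways. Entry starts at age 50, partly to limit radiation risk. Women over 57, or over 50 and without periods for 12 months, count as post-menopausal. The list of accepted contraceptive methods is restrictive, pregnancy and planned pregnancy are exclusions, and Section 1.4 states that the radiosensitive group has largely been kept out. All of this stands, and it is why the expected number is so small.

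Second, the laboratory review before the baseline scan is tied in Section 3.1 to exclusion criterion 8, so its main purpose is to avoid scanning patients who will fail eligibility. It is not presented as a pregnancy check. That is fair as to intent. Even so, hCG is among the results reviewed, so the first scan has a recent test behind it and the second does not.

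Third, a pregnancy could come to light through the physical examination or adverse-event questioning at treatment visits, and the separate MSCT manual, which is not available here, may require a check before scanning. Either is possible, but the Protocol itself requires no test before the second scan.

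Fourth, Section 5.8.1 matters only if a patient known to be pregnant were actually sent for CT, which Section 1.4 should discourage. This limits the practical risk but leaves the wording wrong.

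**Conclusion.** The concern holds, as a minor safety point. For patients on schedule, the second CT pair falls 78–84 days after the last pregnancy test, against 7–15 days for the baseline scan, and the next test follows the last dose by 11–20 days. These figures rest only on the Protocol's visit windows. The expected number of pregnancies, 0 to 0.015, rests on assumed inputs and indicates only that the event would be rare. The missing pregnancy exception in Section 5.8.1 needs correcting however rare the event is. The analysis and its interpretation are not affected.

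**What to change.** 1. In Table 2 footnote a, and to match in Sections 4.1, 5.1 and 6.4.9, add for women of child-bearing potential: *a urine pregnancy test on the day of the second MSCT, before scanning; no scan unless the result is read as negative.*
2. In Section 5.8.1, after the existing exception ("with the exception of MSCT for patients who have had less than 2 months of randomised treatment"), add: *or who are pregnant.*
3. Optionally, add the same dipstick at Visits 4 and 5, so that the rule in Section 13.3.1 can be triggered by a scheduled test during dosing. Urine is already tested on site at these visits: "Urinalysis will be performed locally at the study site using dipsticks provided by the central laboratory". Section 6.4.9 shows that pregnancy dipsticks come from the same supplier.

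The cost is one to three dipsticks per woman of child-bearing potential, a footnote with matching text in three sections, and one clause. A kit must be available where the scan is done. A positive or unclear result would delay the scan and could cost one Visit 6 value of AWT-Pi10, the primary variable.
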